7.4.5. Pre-specified analysis

A detailed study protocol and statistical analysis plan (SAP) will be written to support both the clinicaltrials.gov registration and publication in top medical journals. Safety and Adverse Events

7.5. Definitions

Unanticipated Problems Involving Risk to Subjects or Others (UPIRTSO)

Any unanticipated problem or adverse event that meets the following three criteria:

- **Serious**: Serious problems or events that results in significant harm, (which may be physical, psychological, financial, social, economic, or legal) or increased risk for the

subject or others (including individuals who are not research subjects). These include: (1) death; (2) life threatening adverse experience; (3) hospitalization - inpatient, new, or prolonged; (4) disability/incapacity - persistent or significant; (5) birth defect/anomaly; (6) breach of confidentiality and (7) other problems, events, or new information (i.e. publications, interim findings, product labeling change) that in the opinion of the local investigator may adversely affect the rights, safety, or welfare of the subjects or others, or substantially compromise the research data, **AND**

- Unanticipated: (i.e., unexpected) problems or events are those that are not already described as potential risks in the protocol, consent document, not listed in the Investigator's Brochure, or not part of an underlying disease. A problem or event is "unanticipated" when it was unforeseeable at the time of its occurrence. A problem or event is "unanticipated" when it occurs at an increased frequency or at an increased severity than expected, **AND**
- Related: A problem or event is "related" if it is possibly related to the research procedures.

Adverse Event

An untoward or undesirable experience associated with the use of a medical product (i.e., drug, device, biologic) in a patient or research subject.

Serious Adverse Event

Adverse events are classified as serious or non-serious. Serious problems/events can be well defined and include;

- death
- life threatening adverse experience
- inpatient hospitalization or prolongation of existing hospitalization
- persistent or significant disability or incapacity
- substantial disruption of the ability to conduct normal life functions
- birth defect/congenital anomaly

and/or per protocol may be problems/events that in the opinion of the sponsor-investigator may have adversely affected the rights, safety, or welfare of the subjects or others, or substantially compromised the research data.

All adverse events that do not meet any of the criteria for serious, should be regarded as **non-serious adverse events**.

7.6. Recording/Reporting of Adverse Events

Anticipated study related risk is limited to potential skin irritation from placement of ECG lead electrode stickers directly on the skin for ECG measurements. No other adverse event is expected in relation to this study.

Reports of skin irritation in relation to ECG electrode stickers will be captured in REDCap.

Adverse events/experiences will only be collected within 3 hours following study interventions or within the duration of the specific clinical encounter where study interventions were

performed (depending on which is longer). An expected hospitalization for childbirth or other pregnancy related complication will be excluded.

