1.4. Risks and Benefits

The risks of this research study are expected to be minimal and represent the general risks associated with prenatal wellness screening and routine medical care. However, there are some risks that are associated with study procedures. Anticipated study related risk includes the potential skin irritation from placement of ECG lead electrode stickers directly on the skin for 12-lead ECG recordings. To minimize risk for skin irritation, the ECG lead electrode stickers will only be placed on the skin for the duration that the ECG is recorded as with standard clinical practice with an estimated duration of contact less than 5 mins.

Another risk in this study is the communication of results for the attention control arm. Two experimental algorithms will be used that predict biological sex and age. There is a potential for discordance in sex to be reported along with large variances in estimated age. The implications of such predictions is not yet known. Study staff will be trained on the algorithms and a study information sheet will be used to describe the study procedures and test results.

As with all research, there is a chance that confidentiality could be compromised; however, we take precautions to minimize this risk.

- All enrolling sites in Nigeria will maintain their own confidential screening logs following local institutional procedures, local regulations and ethics boards requirements.

- Confidentiality of patient information will be maintained by assigning study identifiers to the medical data.
- Digital ECG data will be sent using a secure, encrypted online-based file share service with detailed instructions provided to study sites and as detailed in the study's Manual of Operations. No identifiable data received will be shared external to Mayo Clinic. Only study staff will have access to the data collected.
- Additional Considerations: The following is a list of study participant confidentiality safeguards:
 - **Data flow procedures** – Data identifying participants should not be transmitted from study sites to the Coordinating Center.
 - **Electronic files** – Data identifying participants that are stored electronically should be maintained in an encrypted form or in a separate file with device password protection.
 - **Forms** – Forms or pages containing personal identifying information should be separated from other pages of the data forms and retained in a secure location.

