6.4. Age and Sex ECG Estimation

The application of the AI-ECG algorithms to estimate age and sex will occur at the coordinating center. As such, the estimation will be asynchronous with the clinical visits at each sites. The Coordinating Center will process ECGs as they arrive (~ monthly for each site) and return a report back to study investigators with the model results. These results may be communicated to the participant at a subsequent study visit (at the provider's discretion).

7. Statistical Plan

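### Section 7.6 limits anticipated risk to skin irritation although section 1.4 names result communication as a risk, and no solicited capture is specified for non-serious harm arising after a disclosure visit

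*Combined protocol and SAP*

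**What the plan says.** Section 1.4 (Risks and Benefits) describes skin irritation and then adds: "Another risk in this study is the communication of results for the attention control arm". It explains that the algorithms may report a sex that does not match the participant, or an age far from her own, and concedes that the consequences are unknown. Its safeguards are staff training and an information sheet.

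Section 7.6 (Recording/Reporting of Adverse Events) takes a narrower view: "Anticipated study related risk is limited to potential skin irritation", and then "No other adverse event is expected in relation to this study". The only capture route that it names is for that one event: "Reports of skin irritation in relation to ECG electrode stickers will be captured in REDCap". The collection rule is general and restrictive: "Adverse events/experiences will only be collected within 3 hours following study interventions or within the duration of the specific clinical encounter" in which the intervention took place, whichever is longer.

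Section 6.4 says that age and sex estimates are produced centrally, about monthly for each site and not at the visit itself. It continues: "These results may be communicated to the participant at a subsequent study visit", at the provider's discretion.

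Section 7.5 defines a separate category, unanticipated problems involving risk to subjects or others (UPIRTSO). These must be serious, unanticipated and related to the research. Psychological and social harm are included.

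**The concern.** Two sections of one protocol disagree about what the study's risks are, and the collection rule is built on the narrower account. Skin irritation appears at once and at the site, so a window of hours suits it. Distress, stigma or family consequences after a woman is told that her ECG suggests a different sex or a very different age may appear only once she is home.

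What is at stake is safety ascertainment. If few adverse events are recorded, that may reflect the collection rule and would say little about the effect of disclosure, which the protocol itself describes as unknown. Section 1.4 ties the risk to the attention control arm, but section 3.1 and the schedules in 6.1 give age and sex estimation to both arms.

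**Working it through.** The plan states no figure to reproduce here. The check sets the sections side by side and adds one count.

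**1. Do 1.4 and 7.6 agree on the risks?** No. Section 1.4 names result communication in addition to skin irritation. Section 7.6 limits anticipated risk to skin irritation and expects no other event. Both statements cannot stand.

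**2. Does the window cover a reaction at disclosure?** Yes. Section 6.4 places disclosure at a study visit. Section 5.1 has a 12-lead ECG recorded at every visit, so the window reopens then and lasts at least as long as the encounter.

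**3. Does it cover what arises after that visit?** No. Once 3 hours have passed since the intervention and the encounter is over, section 7.6 collects nothing until the next study intervention.

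**4. Is there another route in the text?**
- The visit lists (6.1 and 6.2.2) contain no adverse-event question. Clinical assessments are height, weight, blood pressure and heart rate.
- New clinical diagnoses are recorded at visits 2 to 7, and records are reviewed for clinical outcomes (6.2). Harm that led to a diagnosis could appear there; undiagnosed distress probably would not.
- The UPIRTSO route in 7.5 has no time window and covers psychological and social harm, but only if it is serious, unanticipated and related.
- Medical monitoring (7.8) refers back to the adverse-event rules and adds no collection of its own.
- Training and the information sheet (1.4) reduce the risk but do not record harm.

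What remains without a specified solicited capture is non-serious, undiagnosed harm after a disclosure visit.

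**5. How many disclosures could there be?** The inputs are 1 to 7 visits per woman (3.3), one ECG per visit (5.1) and disclosure at a later visit (6.4). On that route the last ECG has no later visit, so the maximum is visits minus 1:
- seven visits: 7 − 1 = 6 disclosures
- one visit: 1 − 1 = 0 disclosures

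These are ceilings. The documents give neither the distribution of visits per woman nor the share of results that providers will pass on, so expected exposure cannot be derived, and neither can the rate of harm.

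**The case against.** A reader might infer that harm after the visit would never be collected. The documents do not support that. A serious event may reach the UPIRTSO route, harm that leads to a diagnosis may be recorded at the next visit, and site monitoring (9.1) checks the documentation of unanticipated problems. The roughly monthly turnaround does not show a missed event either. It measures delay from the ECG that produced the result, whereas the window reopens at the visit where the woman hears it.

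A reader might also infer that sites cannot tell whether such harm is unanticipated under 7.5, because 1.4 and 7.6 differ. That fails. The test excludes from the unanticipated category risks described anywhere in the protocol; unanticipated problems are "those that are not already described as potential risks in the protocol" or its related documents. Section 1.4 is part of the protocol. Section 7.5 also treats an event as unanticipated if it is more frequent or more severe than expected, so describing a risk does not close the route.

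Counting seven results per woman would count ECGs and not disclosures, which are discretionary and come later.

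Three further objections have weight. No objective or endpoint concerns the safety of disclosure, and nothing says that a low event count will be offered as evidence of it. The case report forms, additional reporting forms and Manual of Operations are not in the text available and may already hold a suitable field. The protocol rates the study as minimal risk, so a solicited question is partly a matter of preference. These points limit the size of the concern. They do not remove the conflict between 1.4 and 7.6, or the poor fit between the stated window and a risk that the protocol itself names.

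**Conclusion.** The point holds in a limited form. Section 7.6 contradicts section 1.4 on the study's risks. Its window covers an immediate reaction at the disclosure visit but specifies no solicited capture of non-serious distress or social consequences arising after it. Exposure is 0 to at most 6 later-visit disclosures per woman, in either arm, and the event rate is unknown.

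This assumes that results are disclosed only as 6.4 describes and that no unseen form already asks the question. If such a form exists, the gap in capture closes but the wording conflict remains. This is a minor, inexpensive improvement in safety ascertainment. The primary and secondary efficacy analyses and the sample size are unaffected.

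**What to change.** 1. Reconcile 7.6 with 1.4. List harm from communicating age and sex results as an anticipated risk in 7.6, and say in both sections that it applies to both arms.
2. Add one REDCap item at the existing visits 2 to 7, in both arms, asking about any problem since the last visit that the participant links to a reported study result. State in 7.6 that this item is not subject to the 3-hour or same-encounter limit.
3. Keep that limit for device and skin events.
4. First check the case report forms and Manual of Operations. If an equivalent field exists, cite it in 7.6 instead.

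The cost is a wording change, one form item and slightly more data entry, with no new visit or procedure. One limit remains: a result given at a woman's last visit has no later visit at which to ask. With seven visits, the item therefore follows up at most 6 − 1 = 5 of the 6 possible disclosures.

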7.7. Stopping Rules

No study stopping rules are proposed based on the risk profile for the study. In the event the feasibility of the study is not tenable due to challenges in recruitment or other study operational considerations, the study may be terminated at the request of the study PI in conjunction with the institutional review board of record.

7.8. Medical Monitoring

It is the responsibility of the Principal Investigator and site PIs to oversee the safety of the study at his/her site. This safety monitoring will include careful assessment and appropriate reporting of adverse events as noted above.

8. Data Handling and Record Keeping

8.1. Confidentiality

Confidentiality of patient information is maintained by assigning study identifiers to the medical data before data is transmitted to Mayo Clinic. [REDACTED]

[REDACTED] No data received will be shared external to Mayo Clinic. Only study staff will have access to the data collected. The CRF exported from REDCap is attached in the appendix section.

In the event that a subject revokes authorization to collect or use PHI, the investigator retains the ability to use all information collected prior to the revocation of subject authorization. For subjects that have revoked authorization to collect or use PHI, attempts would be made to obtain permission to collect at least vital status (long term survival status that the subject is alive) at the end of their scheduled study period.

8.2. Source Documents

Source data is all information, original records of clinical findings, observations, or other activities in a clinical trial necessary for the reconstruction and evaluation of the trial. Source data are contained in source documents. Examples of these original documents and data records include: hospital records, clinical and office charts, laboratory notes, memoranda, subjects' diaries or evaluation checklists, pharmacy dispensing records, recorded data from automated instruments, x-rays, subject files, and records kept at the pharmacy, at the laboratories, and at medico-technical departments involved in the clinical trial.

Source documents will be stored at each local site according to local data privacy rules and regulations.

All essential study documents will be retained by the local PI in a Participant Binder and generally include the following:

- Source documents
- Signed consent forms

8.3. Case Report Forms

The study case report form (CRF) is the primary data collection instrument for the study. All data requested on the CRF is expected to be recorded. All missing data must be explained. All entries will be documented electronically using REDCap.

Data Management

This study will use REDCap to capture all clinical and study related data entries with the exception of ECGs. REDCap will utilize a user-friendly interface for data collection which will allow data entry by study coordinator/staff at each study site.

Data Tracking, editing, updating and reporting will be tracked in REDCap. For statistical analysis, data can be exported as CSV, SAS or R files for analysis.

ECG Data

The standard 12-lead ECG:

- will be collected and stored using a GE MAC 2000 device. ECGs will be exported from this machine and securely transferred to Mayo Clinic for analysis.

Portable ECGs:

- Data from the AliveCor device will be transmitted via the research study's smartphone/tablet app to the cloud, where it will be password protected via account log-in, and only accessible to the research team for download to the Mayo research server. The AliveCor cloud server will only be utilized during the duration of the research study and is not accessible to external parties. The AliveCor cloud server will only be utilized during the duration of the research study and is not accessible to external parties.
- Raw data from the Eko DUO Stethoscope device will be transmitted via the research study's smartphone/tablet app to the cloud, where it will be password protected via account log-in, and only accessible to the research team for download to the Mayo research server. The Eko DUO cloud server will only be utilized during the duration of the research study and is not accessible to external parties.

Echocardiographic data

Echocardiographic data will be stored in accordance with local standard data protection and privacy rules and established clinical process at each participating site. Specific echo measurements will be abstracted from the echocardiogram report and entered into REDCap following review by an echo-cardiologist (in accordance with the American Society of Echocardiography guidelines) at each participating site.

Quality Control Procedures

Instructions for use for the ECG devices, data entry forms on REDCap and additional reporting forms are attached in the appendix section.

Study-Specific ECG Device Use Guidelines

The following Instructions for Use (IFU) are attached in the appendix:

- KardiaMobile 6L IFU
- EkoDuo IFU
- GE ECG machine IFU

Data and Form Checks

Data quality control checks will be performed in REDCap to identify potential data anomalies, such as: missing data, outliers, illogical dates, erroneous entries and other data inconsistencies. Data quality checks have also been built into REDCap to prevent entry of erroneous data such as preventing “text” entries in a numeric field and use of pre-specified checkboxes to limit data entry errors.

8.4. Records Retention

The study investigators will maintain records and essential documents related to the conduct of the study. These will include subject case histories and regulatory documents.

After the study ends, study staff shall maintain participant forms in a secure location for 3 years, as indicated by the protocol, federal regulations, and IRB guidance.

9. Study Monitoring, Auditing, and Inspecting

9.1. Study Site Monitoring Plan

Site monitoring conducted by the coordinating center (Mayo Clinic) will take place every quarter via virtual video conferencing in addition to one more in-person site visit during the study period.

During the scheduled monitoring visits, the coordinating site will:

- Ensure the rights and safety of participants
- Confirm that the study is conducted in accordance with guidelines
- Ensure maintenance of required documents
- Verify adherence to the protocol
- Monitor the quality of data collected
- Ensure accurate reporting and documentation of unanticipated problems

During monitoring visits, the data recorded on CRFs will be reviewed to ensure:

- Informed consent has been obtained and documented in accordance with IRB regulations
- There are no omissions in the reports of specific data elements

- Missing examinations are indicated
- Participant disposition when exiting the study is accurately recorded

Site investigators must ensure that the study coordinator or identified study staff has access to all study documents, including informed consent forms, intervention accountability records, and source documents.

Once the site visit is complete, a site monitoring report will be drafted to provide feedback regarding any problems or issues that may have been uncovered during the visit. The report will state the problems uncovered during the visit and describe recommendations to correct them. A timeline will be included in the report to ensure that the follow-up of the issues is completed and implemented into the study's procedures.

10. Ethical Considerations

This study is to be conducted according to United States government regulations and Regulatory standards, Mayo Clinic Institutional research policies and procedures, ethical principles of the International Conference on Harmonization (ICH) as well as local (Nigeria) federal, institutional procedures, regulations and ethics boards requirements.

This protocol and any amendments will be submitted to a properly constituted local Institutional Review Board (IRB) for formal approval of the study. The decision of the IRB concerning the conduct of the study will be made in writing to the investigator before commencement of this study.

All study participants will be provided a consent form describing this study and providing sufficient information for subjects to make an informed decision about their participation in this study. This consent form will be submitted with the protocol for review and approval by each local IRB for the study. The formal consent of a subject, using the approved IRB consent form, must be obtained before that subject undergoes any study procedure. The consent form must be signed by the subject or the subject's legally authorized representative, and the individual obtaining the informed consent.

